Key cognitive functions important for driving will also be assessed on Days 1 and 7 with a pencil and paper Digit Symbol Substitution Test (DSST), as well as with the Cogstate battery of cognitive tests. The Cogstate battery will include the Detection Test (psychomotor function), Identification Test (attention), One Back Test (working memory), Groton Maze Learning Test (executive function), and Chase Test (visual motor control). In addition, blood pressure and heart rate will be measured repeatedly after each dosing. Symptoms of suicidal ideation, self-harm, and suicidal behavior will be monitored repeatedly using the C-SSRS. The MADRS will be repeatedly administered and evaluated as an exploratory assessment. Pharmacokinetic sampling will be performed daily during the inpatient period except on Day 0. Subjects will be discharged in the morning on Day 8 pending approval by a physician. Before discharge, the subject and the Investigator will be asked separately whether they believe the study drug could be safely administered at home based on their experience with dosing during the inpatient stay.

There will be an outpatient safety follow-up of 1 week after the last study drug administration. During this period, there will be a remote assessment of the 20-item Physician Withdrawal Checklist (PWC-20) by telephone on Day 10 and a follow-up visit on Day 14.

At the conclusion of Part A, an independent Data Safety Monitoring Board (DSMB) will review the data from Part A. The outcome of the DSMB review will be submitted to the Food and Drug Administration before proceeding with Part B.

Part B

Part B will comprise 3 phases:

- Screening phase that will last up to 28 days (Days -28 to -1).

- Four-week double-blind treatment phase (4 weeks of dosing and an end of treatment [EOT] visit; Days 1 to 29).
- Posttreatment safety follow-up phase of 2 weeks after last study drug administration (Days 30 to 42).

During Screening, subjects will be assessed for study eligibility and will taper and/or wash out from benzodiazepines, benzodiazepine-like drugs, prescription sleeping aids, and other disallowed drugs, if needed. Eligible subjects will be randomized to receive either placebo or 40 mg CLE-100 once daily in addition to their current oral antidepressant monotherapy for 4 weeks.

Subjects will receive study drug orally once daily (Days 1 to 28).

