For Part B, a fixed sequence gatekeeping (hierarchical) approach will be applied to adjust for multiplicity and to control type I error due to multiple efficacy endpoints testing of the primary and key secondary endpoints. The sequence order is according to the defined order of the primary and key secondary endpoints. If the primary analysis is statistically significant at the 2-sided 0.05 level, the key secondary endpoints will be analyzed sequentially according to their defined order. A key secondary endpoint will be considered statistically significant at the 2-sided 0.05 level only if the previous key secondary or primary

endpoint in the hierarchy is significant at the 2-sided 0.05 level.

The primary estimand for Part B of this study is based on the efficacy assumption (de jure) using the hypothetical strategy. The treatment effect will be attributed to eligible and randomized subjects who have both a Baseline and at least 1 post-Baseline MADRS total score measurement while the subjects are on study drug and hypothetically received study medication for 4 weeks.

An evaluation of the possible impact of missing values on the primary analysis results will be performed.

The treatment policy estimand strategy will also be evaluated as a secondary estimand and is based on the effectiveness assumption (de-facto). The treatment effect will be attributed to eligible and randomized subjects regardless of early treatment discontinuation.

The change in the MADRS total score from Baseline to Week 4 (Day 29) in Part B will be analyzed using Mixed Models Repeated Measures analysis.

The model will use the unstructured covariance matrix, the Restricted Maximum-Likelihood (REML) estimation method, and the Kenward-Roger adjustment method for the degrees of freedom. In the case that the model does not converge, the Maximum-Likelihood estimation method will be used instead of the default REML. If the model still does not converge, then a simpler covariance structure with fewer parameters will be used according to the following order: heterogeneous autoregressive (1), heterogeneous compound symmetry, autoregressive (1), and compound symmetry.

All data collected while the subject is on study drug for all randomized subjects who received at least 1 dose of study drug and have a Baseline MADRS total score will be included in the primary efficacy analysis.

SAMPLE SIZE DETERMINATION:

Part A

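### Does the narrower population in the primary estimand, compared with the primary analysis, let the earliest drop-outs escape the missing-value evaluation?

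*Combined protocol and SAP*

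**What the plan says.** All the relevant text is in the combined protocol and SAP, synopsis, STATISTICAL ANALYSES, Part B.

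- **Primary estimand** (hypothetical strategy): attributed to eligible randomised subjects "who have both a Baseline and at least 1 post-Baseline MADRS total score measurement while the subjects are on study drug", as if they had taken study medication for the full 4 weeks.
- **Missing values:** "An evaluation of the possible impact of missing values on the primary analysis results will be performed". The visible text gives neither a method nor a subject set.
- **Secondary estimand** (treatment policy): "The treatment effect will be attributed to eligible and randomized subjects regardless of early treatment discontinuation". It carries no post-Baseline condition.
- **Primary model:** change in MADRS to Week 4 "will be analyzed using Mixed Models Repeated Measures analysis". On covariance, estimation and degrees of freedom, the plan then states: "The model will use the unstructured covariance matrix, the Restricted Maximum-Likelihood (REML) estimation method, and the Kenward-Roger adjustment method".
- **Data for the primary analysis:** on-drug data "for all randomized subjects who received at least 1 dose of study drug and have a Baseline MADRS total score".

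**The concern.** The estimand and the analysis meant to estimate it do not describe the same people. Having at least one on-drug rating after Baseline is a post-randomisation event, and treatment can influence it: a subject who tolerates the drug badly may stop before being rated. Selecting on such an event weakens the comparison that randomisation protects.

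The practical worry is the missing-value evaluation. It exists to show whether the primary result survives less favourable assumptions about drop-outs, and subjects lost before their first on-drug MADRS have the most missing data. If the estimand's wording governed that evaluation, they would be left out and the result could look sturdier than it is. If the analysis sentence governed, they would be in.

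**Working it through.** **1. Who is affected.** Setting the two sentences side by side, the subjects at issue have been randomised and dosed, have a Baseline MADRS, and have no on-drug MADRS afterwards. The analysis sentence includes them and the estimand sentence does not. Their number is not given.

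**2. Primary model.** The response is change from Baseline. A subject with no post-Baseline value has no response, adds no row and contributes no term to the restricted likelihood. The fit is therefore identical with or without such subjects. A check on one simulated data set (61 per arm, four visits, unstructured covariance, REML) agrees:

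| Subjects supplied | Difference at last visit | SE | REML objective |
|---|---|---|---|
| 122 | -4.337 | 1.802 | 2090.939 |
| 118 (the 4 with no post-Baseline value removed) | -4.337 | 1.802 | 2090.939 |

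This equality would not hold exactly if Baseline were modelled as a response, but the plan specifies change from Baseline. The planned sample size of 122 cannot be re-derived, because its effect size and SD are not visible. It is not at issue here; only the 61 per arm is used below.

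**3. Which set the missing-value evaluation uses.** The plan says the evaluation concerns the primary analysis results. The only sentence that says whose data enter the primary efficacy analysis is the wider one. Read together, they place the earliest drop-outs inside the evaluation.

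**4. Size if the narrow reading were taken.** Assume a penalty of delta points added to imputed Day 29 values in the active arm only. Let k be the active subjects with no on-drug post-Baseline MADRS and m the later active drop-outs. None of k, m, delta or the method is in the documents.

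- Shift under the analysis wording: delta × (k + m)/61
- Shift under the estimand wording: delta × m/(61 − k)

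| k | m | delta | Analysis wording | Estimand wording | Gap | Ratio of imputed shares |
|---|---|---|---|---|---|---|
| 1 | 9 | 5 | 5 × 10/61 = 0.820 | 5 × 9/60 = 0.750 | 0.070 | 1.09 |
| 3 | 6 | 5 | 5 × 9/61 = 0.738 | 5 × 6/58 = 0.517 | 0.220 | 1.43 |
| 6 | 3 | 8 | 8 × 9/61 = 1.180 | 8 × 3/55 = 0.436 | 0.744 | 2.70 |

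Giving k active subjects zero treatment effect instead multiplies the estimated effect by (61 − k)/61, which is 0.984, 0.951 or 0.902 for k = 1, 3 or 6. Omitting them leaves the multiplier at 1.

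**5. Cases where the gap is zero.**

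- The evaluation refits likelihood models: zero, by step 2.
- The same delta is applied in both arms with equal k and m: each arm moves by the same amount under either wording, so the difference between arms does not move.
- Imputation under missing at random (delta = 0): a simulation of 150 trials with k = 3, m = 6 and an assumed SD of 9 gave a gap of 0.003 (Monte Carlo SE 0.014), which is indistinguishable from zero.

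The range therefore starts at zero, and its upper end is set by assumptions alone. The 2.70 ratio needs twice as many drop-outs before the first on-drug rating as after it, which nothing in the documents supports. As a tipping-point factor, the ratio also ignores the change in standard error.

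**The case for a change.** The best case for a change is that the two sentences plainly disagree, that no blacked-out text interrupts either, and that the estimand's condition is unnecessary. The hypothetical strategy already deals with early stopping by supposing 4 weeks of treatment. Because the treatment-policy estimand has no such condition, the two estimands differ in population as well as strategy. The population of a robustness check is best fixed before unblinding, and the repair would cost one line.

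The mismatch stands, and the estimand sentence is the weaker of the two. The consequence does not follow. The visible text links the missing-value evaluation to the primary analysis, so an analyst has a stated set to use and it is the more inclusive one. The treatment-policy estimand also covers early drop-outs in its own right.

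The supplied document is a synopsis with text removed. It refers to a Safety Analysis Set for Part A without defining it, so definitions of analysis sets evidently sit elsewhere; the set and method for the missing-value evaluation may sit there too. The same applies to how long after the last dose a rating still counts as on-drug for someone who stops early. For completers there is no doubt, since Day 29 lies within the treatment phase: "Four-week double-blind treatment phase (4 weeks of dosing and an end of treatment [EOT] visit; Days 1 to 29".

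The wider set also conditions on something after randomisation, namely a first dose. Under blinding, receiving that dose should not depend on the arm, so this is a much milder condition than having an on-drug rating.

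**Conclusion.** No change to the plan follows. The estimand sentence is worded more narrowly than the analysis sentence, but the primary estimate, standard error and test are the same under both. Alpha, the testing hierarchy and the sample size are untouched. On the natural reading, the missing-value evaluation already includes subjects with no on-drug post-Baseline MADRS.

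A difference would need both the less natural reading and an imputing or shifting method that treats the arms unequally or meets unequal drop-out. Its size then runs from zero upward and cannot be estimated from the documents; the 0.07 to 0.74 points shown belong to one assumed method. The conclusion rests on change from Baseline being the model response and on the evaluation following the primary analysis set. This is a wording gap that analysts can fill sensibly, and harmonising it brings no demonstrated gain in the result.

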The subject will also be provided an information sheet with instructions for the administration of study drug at home. The Investigator or key clinical staff will be available 24 hours a day/7 days a week for the duration of the study, and the relevant phone number will be provided on the information sheet. The subject will also be informed at discharge that an early refill will only be given under special circumstances and upon approval by the Sponsor on a case-by-case basis.

and to not use benzodiazepines, benzodiazepine-like drugs, or sleeping aids (either prescription or over-the-counter).

Instructions about driving and operating machinery and warning about the use of sedative drugs during the study treatment period, as well as information on available car services, will be included on the information sheet provided to the subject at discharge at Visit 2.

There will be weekly on-site visits (Visits 3 to 5)

Suicidal ideation, self-harm, and suicidal behavior will be monitored once weekly using the C-SSRS. Pharmacokinetic sampling will be performed at each on-site visit during the 4-week treatment period.

The DSMB will evaluate the unblinded safety data during Part B of the study at intervals predetermined in the DSMB charter. The DSMB will provide their recommendation for the continuation or discontinuation of the study as planned or whether protocol changes are warranted.

DOSAGE FORMS AND ROUTE OF ADMINISTRATION:

CLE-100 is an oral, immediate-release (IR) formulation of esketamine hydrochloride for once daily administration [REDACTED]. For this study, 40 mg IR tablets of CLE-100 will be used.

Part A

In Part A, subjects will be randomized in a 4:1 ratio to the following 2 treatment groups:

- 40 mg CLE-100 (12 subjects).
- Placebo (3 subjects).

Part B

In Part B, at Visit 2 predose, subjects will be randomized in a 1:1 ratio to the following 2 treatment groups:

- Placebo (61 subjects).
- 40 mg CLE-100 (61 subjects).

The study drug will be administered in addition to the subject's current oral antidepressant monotherapy that must be kept at a stable therapeutic dose throughout study participation.

EFFICACY VARIABLES IN PART B:

The primary efficacy endpoint for Part B of this study is the change from Baseline to Week 4 (Day 29) in the MADRS score.

The key secondary efficacy endpoints for Part B of this study include the following:

- Change in the self-rated SDQ from Baseline to Week 4 (Day 29).

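### Does the secondary treatment-policy estimand lack the off-drug Week 4 MADRS data it needs?

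*Combined protocol and SAP*

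**What the plan says.** All references are to the Synopsis, the only part of the protocol in the public text.

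- **STATISTICAL ANALYSES, Part B, primary analysis.** The primary estimand is hypothetical (de jure). Its analysis set is "All data collected while the subject is on study drug for all randomized subjects who received at least 1 dose of study drug", provided that they also have a baseline MADRS. An evaluation of how missing values affect the primary result is planned as well.
- **STATISTICAL ANALYSES, Part B, secondary estimand.** "The treatment policy estimand strategy will also be evaluated as a secondary estimand and is based on the effectiveness assumption (de-facto"). It concerns randomized subjects whether or not they stop early: "The treatment effect will be attributed to eligible and randomized subjects regardless of early treatment discontinuation". The visible text gives no estimator, data rule or imputation method for it.
- **STUDY DESIGN AND DURATION, Part B, phases.** Treatment is a "Four-week double-blind treatment phase (4 weeks of dosing and an end of treatment [EOT] visit; Days 1 to 29"), with dosing described as "Subjects will receive study drug orally once daily (Days 1 to 28"). It is followed by a "Posttreatment safety follow-up phase of 2 weeks after last study drug administration (Days 30 to 42").
- **STUDY DESIGN AND DURATION, Part B, visits.** "There will be weekly on-site visits (Visits 3 to 5"), after which the sentence breaks off.

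No visible passage describes what happens to a subject who stops study drug early. No schedule of assessments or discontinuation section is included in the public text.

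**The concern.** A treatment-policy effect at Week 4 includes the Day 29 MADRS of subjects who are no longer taking study drug. The phase list offers only one period after drug, it is called a safety follow-up, and it is two weeks long from the last dose. If that is all an early stopper gets, someone who stops in the first two weeks is out of the study before Day 29. Someone who stops later is in a phase whose name suggests no efficacy rating.

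If the off-drug values were then filled in from on-drug data under missing at random, the de-facto result would come close to the de-jure one. The estimand meant to show whether the benefit survives discontinuation would be reported as effectiveness without showing it. Ratings that are not taken during the trial cannot be recovered later, so the question is worth asking.

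**Working it through.** **1. The plan's own calendar.** Dosing runs to Day 28, the end-of-treatment visit is on Day 29, and follow-up is two weeks from the last dose. 28 + 14 = 42, which reproduces the end of the range Days 30 to 42. The range is the schedule of a subject who takes all doses. It sets no exit rule for someone who stops early, and it does not say that the remaining weekly visits or the Day 29 visit are cancelled.

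**2. The same window counted from an individual last dose.** Suppose the two weeks do run from each subject's own last dose on Day L and nothing else applies. The window reaches Day 29 if L + 14 ≥ 29, that is, if L ≥ 15.

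| Last dose (Day L) | Window ends (L + 14) | Reaches Day 29? |
|---|---|---|
| 1 | 15 | no |
| 7 | 21 | no |
| 14 | 28 | no |
| 15 | 29 | yes |
| 21 | 35 | yes |
| 28 (full course) | 42 | yes |

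Of the 27 possible early last-dose days (1 to 27), 14 fall short and 13 (Days 15 to 27) keep Day 29 inside the window. Even on this strict reading, it does not follow that early stoppers as a group are gone by Week 4.

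**3. How many subjects that could be.** The stopping rate is not given. Assume 5% to 20%, spread evenly over Days 1 to 27.

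- Early stoppers: 122 × 0.05 = 6.1, up to 122 × 0.20 = 24.4.
- Window ends before Day 29: 6.1 × 14/27 = 3.2, up to 24.4 × 14/27 = 12.7.
- Share of all subjects: 0.05 × 14/27 = 2.6%, up to 0.20 × 14/27 = 10.4%.

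**4. The feared bias and what it needs.** The effect size, SD and drop-out allowance are not visible in SAMPLE SIZE DETERMINATION, so the 122 can only be solved backwards. With 61 per arm, 80% power, two-sided 0.05 and no drop-out, the standardized effect is (1.960 + 0.842) × √(2/61) = 0.507, or 0.511 with the t distribution. With an assumed SD of 9, 0.511 × 9 = 4.6 points. If a fraction p of the active arm stops and returns to a placebo-like level, the treatment-policy effect is 4.6 × (1 − p):

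- p = 10%: 4.6 × 0.9 = 4.14. An estimate of 4.6 would be too high by p/(1 − p) = 0.10/0.90 = 11%.
- p = 20%: 4.6 × 0.8 = 3.68. The excess is 0.20/0.80 = 25%.

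The arithmetic is correct, but it needs three conditions together: no off-drug Week 4 rating is obtained for any stopper, stoppers on active drug lose the whole effect, and the estimator uses on-drug data under missing at random. The visible text states none of them.

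**5. The two data descriptions side by side.** The primary analysis is limited to "All data collected while the subject is on study drug". The secondary estimand is defined without regard to discontinuation. If no MADRS were taken after stopping, the on-drug limit would have little to exclude and the two estimands would share the same data. The limit makes better sense if off-drug ratings exist and are left out of the hypothetical estimand only. This is an indication, not proof, but it points away from the concern.

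**6. Whether the estimand could be estimated.** Missing off-drug values make a treatment-policy estimate depend on assumptions; they do not make it impossible. Reference-based imputation, for example, borrows from the control arm and needs no off-drug ratings. Since no estimator is visible for this estimand, nothing shows that on-drug data would have to be used.

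**The case for a change.** The best case for the concern is that neither reading of the follow-up phase tells a site to obtain an off-drug Day 29 MADRS. If the window runs from the last dose, those who stop on Days 1 to 14 leave it too soon, and those who stop later are in a phase labelled safety. If the calendar days govern, the time between stopping and Day 30 is undescribed. The on-drug restriction could be standard wording for a hypothetical estimand, so it does not prove that off-drug ratings are taken. The planned missing-values evaluation is tied to the primary result and says nothing about outcomes after stopping.

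All of this is fair as a description of what the visible text leaves open, and that much stands: it does not say whether MADRS continues to Day 29 after discontinuation, or how the treatment-policy effect is estimated. It does not establish that ratings stop. The public text is a synopsis whose visit description is cut off and whose sample-size text has gaps, and it refers to an Appendix H that is not included. The place where a plan would normally answer the question is not visible, and text removed from the public copy cannot be counted as missing from the plan.

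The claim that the treatment-policy estimand is the plan's only check on the primary analysis also fails, because the missing-values evaluation is a second one, even though it addresses a different question.

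**Conclusion.** The concern does not hold. No stated rule ends MADRS ratings when study drug ends, none excludes efficacy ratings from follow-up, and none prescribes on-drug data for the secondary estimand. The absence of off-drug Week 4 data is inferred from silence in an incomplete synopsis, while the on-drug limit on the primary analysis leans the other way.

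The consequence would in any case be bounded. On the strictest reading of the follow-up window, about 3 to 13 of 122 subjects (2.6% to 10.4%) would leave before Day 29, assuming 5% to 20% early stopping spread evenly over Days 1 to 27. The 11% to 25% overstatement would arise only under the three conditions in step 4, and for 10% to 20% stopping. The primary hypothetical estimand uses on-drug data and is unaffected. The fixed testing sequence covers the primary and key secondary endpoints and does not list the treatment-policy estimand.

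Whether post-discontinuation ratings and the estimator are specified is a matter to look up in the full protocol and SAP. It is not an error shown in this text. This conclusion rests on the visible synopsis; a section in the full protocol that ends efficacy ratings when drug is stopped would reopen the question.

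### Does limiting the primary analysis to on-drug data exclude the Day 29 MADRS, when dosing ends on Day 28?

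*Combined protocol and SAP*

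**What the plan says.** Four statements in the synopsis bear on this point.

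- **Data rule** (Statistical Analyses, Part B): the primary efficacy analysis includes "All data collected while the subject is on study drug for all randomized subjects" who took one dose or more and have a Baseline MADRS total score.
- **Dosing** (Study Design and Duration, Part B): "Subjects will receive study drug orally once daily (Days 1 to 28".
- **Phases** (same section): the double-blind treatment phase is described as "4 weeks of dosing and an end of treatment [EOT] visit; Days 1 to 29". Safety follow-up covers Days 30 to 42.
- **Endpoint** (Efficacy Variables in Part B): the primary endpoint is "the change from Baseline to Week 4 (Day 29) in the MADRS score". Statistical Analyses, Part B repeats Day 29 as the time point for the mixed model for repeated measures.

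The same statistical section defines two estimands. The primary one is hypothetical and supposes that subjects took study medication for the full 4 weeks. The secondary one follows the treatment policy strategy and counts subjects whether or not they stopped early. The public text gives no number of days after the last dose within which a MADRS rating still counts as on-drug.

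**The concern.** The last scheduled dose and the primary assessment fall on different days. If on-drug meant only days on which a tablet is taken, no completer's Day 29 score would qualify and the Week 4 contrast could not be estimated. If it meant anything within Days 1 to 29, a subject who stopped on Day 10 and was rated on Day 15 would contribute an off-drug score to an analysis built on the hypothetical estimand. Neither reading gives the intended data set, so the rule looks defective.

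The rule decides which observations enter the primary test, and the fixed-sequence procedure makes every key secondary test depend on that result. A cutoff chosen after unblinding could move early stoppers' ratings in or out. If stopping differed by arm, that choice could favour one arm.

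**Working it through.** This is a question of dates and wording, so the check is to set the statements side by side. The plan gives no figure to reproduce on this point.

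**1. Calendar for a completer**
- Last scheduled dose: Day 28. Primary MADRS: Day 29. Gap: 29 − 28 = 1 day.
- Treatment phase: Days 1 to 29. Day 29 is its last day.
- Follow-up phase: Days 30 to 42. Day 29 is one day before it starts.

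The document's own division of time therefore puts the Day 29 rating in the treatment period.

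**2. Three readings of on-drug**

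| Reading | Completer, Day 29 | Stopped Day 10, rated Day 15 | Fits the rest of the plan? |
|---|---|---|---|
| Tablet-taking days only | out | out | No: empties the Week 4 analysis that the same section specifies |
| Any rating in Days 1 to 29 | in | in | No: admits off-drug data under a hypothetical estimand |
| Subject has not stopped treatment early | in | out | Yes |

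The third reading is the ordinary one. The rule is written about the subject's status, not about a study phase. The event that separates the two estimands is early stopping of treatment. A subject who took the planned course and attends the scheduled end-of-treatment visit has had no such event.

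**3. Size under the rejected readings**
- Tablet-taking days only: 0 of up to 122 on-schedule Day 29 scores would be usable. The figure only restates a reading that the document rules out.
- Any rating in Days 1 to 29: the documents give no dropout rate. Assuming 10% to 20% early stopping, 0.10 × 61 = 6.1 and 0.20 × 61 = 12.2, so about 6 to 12 subjects per arm. This is an upper range, because only those rated after stopping would contribute.

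Neither figure measures a fault in the plan as ordinarily read.

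**4. Would a fixed one-day rule do better?**

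The obvious replacement is to count ratings from first dose through one day after the last dose. Applied to two completers:
- Misses only the Day 28 tablet, rated Day 29: 29 − 27 = 2 days, so the primary score is dropped.
- Takes the Day 28 tablet, visit slips to Day 30: 30 − 28 = 2 days, so the primary score is dropped.

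Both scores belong in the analysis. A strict one-day limit would lose valid completer data that the present wording keeps.

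**5. What the missing cutoff affects**

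It affects only ratings made soon after an early stop. On-site visits during treatment are weekly, so a cutoff shorter than a week could bring in at most one scheduled visit per early stopper.

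**The case for a change.** The best case for a change concerns early stoppers. Placing Day 29 in the treatment phase settles matters for completers, but that phase is counted in study days, whereas on-drug status depends on each subject's own last dose. Only a rule tied to that dose separates the data of the two estimands exactly, and none appears in the public text. The same phrase also enters the description of the primary estimand, which requires a post-Baseline MADRS obtained on drug, so it bears on who counts as well as on which ratings count. A sentence written before unblinding would be cheap and would remove any room for choice.

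Part of this stands: no number of days is given, and stating one would be tidy. The rest is weaker.

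- The contrast between the two estimands already ties on-drug status to the subject's own stopping of treatment, so off-drug ratings are excluded in principle without a stated number.
- Only a synopsis with visible gaps is public. It shows no visit windows, schedule of assessments or detailed analysis-set definitions, which is where such a cutoff would normally sit. Its absence from the plan cannot be established.
- The documents do not say that stopping is expected mainly on active drug, and they describe no early-termination rating whose timing could be exploited.

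**Conclusion.** The concern does not hold. The rule does not remove the primary endpoint: Day 29 is the last day of the stated treatment phase and the named time point of the primary model, and completers lose no scores under the ordinary reading. That reading also excludes ratings after early stopping, as the hypothetical estimand requires.

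What remains is a detail that analysts would fill sensibly when they derive the on-treatment flag: the cutoff after an early stopper's last dose. Its effect cannot be sized, because the public text gives neither a dropout rate nor the timing of ratings after stopping. The range of 6 to 12 subjects per arm rests on an assumed 10% to 20% early stopping and on a reading rejected above.

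If the full SAP is silent, an optional note could say that completers' scheduled end-of-treatment rating counts as on-treatment, with allowance for the visit window and a missed final dose, and from what point early stoppers' ratings serve only the treatment-policy analysis. The conclusion assumes that on-drug carries its ordinary sense of not having stopped treatment early, which the two estimand definitions support.
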